## **2. Statistical Analysis Plan**

Comparative statistics were completed between the control group and intervention groups using the student t-test. P-values <0.05 were considered statistically significant. Analyses were completed in RStudio (v1.2.1335).

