## **1. Study Protocol**

### **Hypothesis and Objectives**

The primary objective of this study is to investigate the effectiveness of the addition of a written action plan (WAP) on patient understanding and management of HS.

Hypothesis 1: Subjects randomized to the intervention group will self-report increased understanding of their HS and management plan, as compared to the verbal consultation (VC).

The secondary objective is to investigate the patients' comfort level in following their individualized WAPs at home.

Hypothesis 2: Subjects receiving a WAP will self-report increased comfort level in managing their HS at home with guidance from a WAP.

The tertiary objective is to investigate whether patients randomized to the control group prefer VC alone, WAP alone, both VC and WAP combined, or neither the VC nor the WAP.

Hypothesis 3: Subjects randomized to the control group will prefer their providers to use a combination of VC and WAP during their office visits.

The quaternary objective is to investigate the patients' anxiety level in managing their HS at home.

Hypothesis 4: Subjects receiving a WAP will self-report lower levels of anxiety in managing their HS at home.

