### **Study Design and Procedures**

Patient recruitment will take place during a routine dermatology. If the HS patient meets the inclusion criteria, he/she will be approached by a study coordinator about this study. If he/she agrees, he/she will sign an informed consent form.

Subjects will then be randomized to one of two groups:

- A control group – VC alone
- An intervention group – VC with WAP

In order to randomize subjects, randomization lists, which are concealed to all parties involved in this study, will be created using a computer software program. As each subject is enrolled, they will be assigned a subject number. After assignment of a subject number, the investigators will refer to the computer-generated randomization scheme corresponding to the assigned subject number to complete the randomization process.

After group assignment, the study coordinator will administer Survey A which will take approximately 10 minutes to both groups. All subjects will be asked to refrain

from asking any questions regarding HS or its treatment until the end of the office visit to ensure controlled delivery of information to all subjects.

The principal investigator will then conduct a routine office visit for the HS patients, consisting of an introduction, history taking, and assignment of Hurley stage. Next, the subjects in the control and intervention groups will receive an individualized VC and VC+WAP, respectively. Subjects from both groups will then complete Survey B which will take approximately 10 minutes. At the completion of Survey B, subjects in the interventional group will have completed the study. Those in the control group will then receive a VC+WAP, followed by completion of Survey C which will take approximately 10 minutes. This is to ensure that all subjects receive the same caliber of care. All Surveys and WAP documents that will be used in our study of written action plans in hidradenitis suppurativa are a standard of care intervention.

Information collected into the medical record during the routine office visit (specifically duration of disease, tobacco use, and disease severity) will be used for this research.

Both groups will take Survey D at a routine follow up visit. Survey D (which will take approximately 10 minutes) is to evaluate if the action plan has had any long-term impact or if it results in behavior change.

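### Does the SAP need a stated test and success criterion for Hypothesis 3, the control group's preference among four options?

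*Combined protocol and SAP*

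**What the plan says.** Under Hypothesis and Objectives, the protocol's tertiary objective is to find out "whether patients randomized to the control group prefer VC alone, WAP alone, both VC and WAP combined, or neither the VC nor the WAP". The prediction made in Hypothesis 3 is this: "Subjects randomized to the control group will prefer their providers to use a combination of VC and WAP during their office visits".

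Under Study Design and Procedures, both groups complete Survey B after their consultation. Then, for controls only: "Those in the control group will then receive a VC+WAP, followed by completion of Survey C". Both groups take Survey D at a later routine visit. The section does not say which survey carries the preference question.

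The SAP is three sentences long. The first gives the method: "Comparative statistics were completed between the control group and intervention groups using the student t-test". The second gives the threshold: "P-values <0.05 were considered statistically significant". The third names the software. None of them mentions a one-group summary, a reference proportion or a rule for Hypothesis 3.

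**The concern.** Hypothesis 3 is worded as a prediction with a direction, yet the only planned method does not fit it. A Student t-test compares the means of two groups. Here there is one group, and the answer is a category. The significance threshold does not help either, because no test or null value that fits this question is attached to it.

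The worry is that *prefer* could be given its meaning after the data are seen. It could mean that the combination is chosen most often, that it is chosen by more than an equal share of 25%, or that it is chosen by more than half. The same table of answers could then be reported as support under one reading and as no support under another. At stake is the conclusion on one tertiary objective.

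**Working it through.** **Is anything misapplied?** There is no figure in the plan to reproduce: the documents give no sample size, power, effect size or expected proportion. The check is first a matter of setting the texts side by side.

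| Element | Hypothesis 3 | SAP method |
|---|---|---|
| Groups | Control only | Control versus intervention |
| Outcome | Choice among four named options | Mean of a numerical score |
| Question | Which option is preferred | Whether two means differ |

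The SAP sentence describes comparisons between the two groups. Hypothesis 3 is not such a comparison, so the t-test is not misapplied to it. The SAP is silent on it.

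**What fills the silence?** The objective lists the options: "prefer VC alone, WAP alone, both VC and WAP combined, or neither the VC nor the WAP". If the item asks each control to pick one, the direct summary is a count and percentage for each option. The option with the largest count is the preferred one in the ordinary sense, and this needs no null value.

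**How much hangs on the other readings?** This is an illustration only; the number of controls and the counts are assumed. Take n = 20 controls: both 9, WAP alone 8, VC alone 2, neither 1 (9 + 8 + 2 + 1 = 20).

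- Most-chosen reading: 9 is the largest count, so the combination is preferred.
- Proportion: 9/20 = 45%. The exact (Clopper-Pearson) two-sided 95% confidence interval is 23.1% to 68.5%, which includes both 25% and 50%.
- Equal-share reading, one-sided exact binomial: P(X ≥ 9 | n = 20, p = 0.25) = Σ (j = 9 to 20) C(20, j) × 0.25^j × 0.75^(20−j) = 0.041.
- Equal-share reading, two-sided exact binomial: p = 0.065.
- Majority reading: 45% is below 50%, so the combination has no majority.

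The answer under the 25% reading therefore changes with sidedness, which the SAP does not state. It can also change with the exact method. For an assumed 16 of 40, the two-sided exact interval starts at 24.9%, just below 25%, while the two-sided exact p-value against 25% is 0.042. For 19 of 50 the interval starts at 24.7% and the p-value is 0.048. Such disagreements arise only once a benchmark has been brought in from outside the plan.

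**Does it reach other results?** Hypotheses 1, 2 and 4 concern understanding, comfort and anxiety. None of them uses the four-option preference item, so nothing here alters them.

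**The case for a change.** The strongest case for a change is that the protocol chose to state a hypothesis, not merely a question, so a reader is entitled to know beforehand what would confirm it. With an assumed 30 controls, 13 choosing the combination (43%) would exceed 25% at one-sided p = 0.022, but 20 (67%) would be needed to exceed 50% at one-sided p = 0.049. Settling the meaning would take two or three sentences and no new data.

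Part of this stands. The SAP should ideally have said that Hypothesis 3 is descriptive, and named the survey, the item and the denominator, since controls answer Surveys B, C and D after a consultation.

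The rest does not carry. The gap between 13 and 20 of 30 comes from two benchmarks that the study never raised. A preference among listed options is ordinarily read as the most frequent choice, and the table answers that directly. Readers can also see all four counts and judge any stricter claim for themselves. Finally, the SAP is written in the past tense, which suggests that the analyses were already done. A definition added now would probably have to be labelled post hoc, so it would clarify the report but would not restore prespecification.

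**Conclusion.** The concern identifies a true omission but does not call for a change to the plan. The SAP leaves out a simple descriptive summary for one tertiary, control-only question, and an analyst would supply that summary in the obvious way: a frequency table of the four options, with the most-chosen one read as the preference. No stated rule produces a wrong answer, and the between-group results are unaffected.

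This rests on two assumptions. One is that the preference item is a single choice among the four options, as the objective's wording suggests; the surveys are not among the documents. The other is that *prefer* carries its ordinary meaning. If a report claimed a majority or a statistically significant preference, that claim would need its own stated benchmark and sidedness, and should be read as post hoc. The size of any effect in this trial cannot be given, because the documents state no number of controls.

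### The SAP does not say which survey score the t-test uses and gives Survey A no role; adjusting Survey B for a matching Survey A item would be a cheap precision gain, provided Survey A was answered before the group was known

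*Combined protocol and SAP*

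**What the plan says.** The Statistical Analysis Plan section gives one between-group method: "Comparative statistics were completed between the control group and intervention groups using the student t-test". It sets significance at P < 0.05 and names R as the software. It names no outcome score, covariate or change score, and it does not say which survey supplies the data.

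Under Study Design and Procedures, allocation comes first. The lists are described as "randomization lists, which are concealed to all parties involved in this study, will be created using a computer software program", and once a subject has a number "the investigators will refer to the computer-generated randomization scheme corresponding to the assigned subject number to complete the randomization process". Then: "After group assignment, the study coordinator will administer Survey A which will take approximately 10 minutes to both groups". The visit follows: "Next, the subjects in the control and intervention groups will receive an individualized VC and VC+WAP, respectively". After that: "Subjects from both groups will then complete Survey B which will take approximately 10 minutes". Survey A is therefore a pre-consultation but post-allocation measure. The text does not say whether the subject or the coordinator knows the group when it is given.

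Under Hypothesis and Objectives, Hypothesis 1 expects that "Subjects randomized to the intervention group will self-report increased understanding of their HS and management plan", and it names verbal consultation as the comparator. Hypothesis 2 reads "Subjects receiving a WAP will self-report increased comfort level in managing their HS at home with guidance from a WAP" and names no comparator. Hypothesis 4, on anxiety, names none either.

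**The concern.** A measure taken from everyone before the consultation is the natural covariate for the same measure taken afterwards. If the SAP gives it no role, the between-group estimate may be less precise than the collected data allow.

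The order of procedures makes this less simple. The two arms receive visibly different care and the outcomes are self-reported, so a subject who already knows the group could answer Survey A differently. An analysis that uses Survey A would then import that difference into the treatment effect. An analysis of Survey B alone would not.

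Because the SAP names no score, a reader cannot tell which of three analyses is meant or available: Survey B alone, change from Survey A to Survey B, or Survey B adjusted for Survey A. They differ in precision, and they differ in how they behave if Survey A was affected by knowledge of the group.

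**Working it through.** **Inputs.** From the documents: two groups, a t-test, and a significance level of 0.05. Not in the documents, so assumed: two-sided testing, 1:1 allocation, n = 30 per arm, true effect d = 0.5 SD, equal SDs scaled to 1, correlation r = 0.3, 0.5 or 0.7 between matching Survey A and Survey B items, and a Survey A shift s of 0.2 SD if the group is known. The plan states no sample size or power, so it has no figure to reproduce.

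**Variance of the three analyses, relative to Survey B alone**
- Survey B alone: 1.
- Survey B adjusted for Survey A: 1 - r², which is 0.91, 0.75, 0.51 at r = 0.3, 0.5, 0.7.
- Change from A to B: 2(1 - r), which is 1.4, 1.0, 0.6. This exceeds 1 whenever r is below 0.5.

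**Power if Survey A is unaffected by group** (non-central t, non-centrality = standardised effect × √(n/2), with √15 = 3.873)
- Survey B alone, 58 df: 0.5 × 3.873 = 1.936, power 48%.
- Adjusted, 57 df: the standardised effect is d / √[(1 - r²)(1 + 1/(2n - 4))], with 1 + 1/56 = 1.018. Non-centrality is 2.012, 2.216, 2.688 and power is 51%, 59%, 75%.
- Change score, 58 df: the standardised effect is d / √[2(1 - r)]. Non-centrality is 1.637, 1.936, 2.500 and power is 36%, 48%, 69%.

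**Break-even.** Adjustment costs one degree of freedom. Equating the adjusted and unadjusted power curves at d = 0.5 gives r = 0.255, 0.135, 0.103 for 10, 30, 50 per arm. Below these values adjustment loses a little: at r = 0 with 30 per arm, power is 47.1% against 47.8%.

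**If knowing the group shifts Survey A by s in the intervention arm**
- Survey B alone: no bias from a shift confined to Survey A, and type I error stays near 5%.
- Adjusted: bias = -r × s = -0.06, -0.10, -0.14. With no true effect, type I error is about 6%, 7%, 11%. With d = 0.5, the estimate falls to 0.44, 0.40, 0.36 and power to about 41%, 41%, 47%. With s = -0.2 the estimate rises to 0.56, 0.60, 0.64.
- Change score: bias = -s = -0.20 whatever r is. Non-centrality under no effect is 0.2 / √[2(1 - r)] × 3.873 = 0.655, 0.775, 1.000, and type I error is about 10%, 12%, 17%.

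**Can the Survey A data show whether a shift occurred?** A t-test comparing Survey A between arms has non-centrality 0.2 × 3.873 = 0.775 and 12% power with 30 per arm. A non-significant result is therefore little reassurance.

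**The case against.** The strongest reply is that nothing is wrong. A randomised comparison of Survey B by t-test is valid, and leaving out a covariate biases nothing. The benefit also depends on facts the documents do not give: a matching item, r, the sample size, and when the group was disclosed. At r = 0.3 the gain is only about 3 power points. The SAP is in the past tense, so the analysis may already be finished. All of this stands, and it limits the point to an inexpensive, conditional improvement.

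Three stronger readings are tempting, and the documents do not support them.
- A reader might infer that the planned test ignores Survey A. The SAP names no score, and Hypotheses 1 and 2 speak of an increase, so a t-test on change from Survey A cannot be excluded. What can be said is that no use of Survey A is specified.
- A reader might infer that Survey A is contaminated because it follows allocation. The text does not say that the subject or the coordinator knew the group then. Concealment of the lists does not settle this either way.
- A reader might infer that Hypotheses 1, 2 and 4 all lose precision. Only Hypothesis 1 names the verbal-consultation comparator. Controls also receive a written plan before Survey C. The part of Hypothesis 2 about guidance from a written plan may have no Survey A counterpart, and nor may the management-plan part of Hypothesis 1, because the individualised plan is delivered after Survey A.

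One refinement also stands. Strictly, adjustment needs Survey A answers to be unaffected by group. Answering before disclosure guarantees that, but it is not the only way it could be true.

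**Conclusion.** The point holds as a conditional improvement. The SAP should say which score is tested and what part, if any, Survey A plays.

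The possible gain runs from about 3 to 27 power points (48% to between 51% and 75%) for r from 0.3 to 0.7, under the assumed 30 per arm and 0.5 SD effect. It needs three things: a matching item, Survey A unaffected by group, and r above about 0.14 at that sample size. The documents establish none of them. If the second fails, adjustment is biased by about -r × shift, and at the assumed 0.2 SD shift in favour of the intervention arm the power gain disappears. A change-score test fares worse on bias, and it is less precise than the plain t-test when r is below 0.5. The t-test on Survey B is therefore the safe default.

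**What to change.** 1. Name the Survey B score as the outcome for Hypothesis 1. Do the same for Hypotheses 2 and 4 only where a between-group Survey B comparison is intended and Survey A holds a matching item.
2. For patients not yet enrolled, give Survey A before allocation.
3. Where Survey A holds the same item and was answered before the subject and the coordinator knew the group, fit a linear model of Survey B score on group and Survey A score. Report the adjusted difference with its 95% CI, and keep the t-test on Survey B as a sensitivity analysis.
4. Otherwise, make the unadjusted t-test on Survey B the main analysis. Establish non-disclosure from study records and not from a non-significant Survey A comparison.
5. If the analysis is already complete, label any adjusted result post hoc.

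Cost: a few sentences in the SAP, one extra model in R, a small change in the order of procedures, and a check on when the group was disclosed. No new data are needed. The documents mention no record of disclosure; if none exists, step 4 applies. The statistical downsides are one degree of freedom (under 1 power point at d = 0.5 with 10 or more per arm, even at r = 0) and the bias of about -r × shift if step 3 is applied when the group was in fact known.
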